7.2.2 Clinical Data

Clinical assessments of study participants at the times of screening, inpatient studies and outpatient follow-up will be performed by Malian physicians (likewise blinded to the treatments the participants have received) using the Case Report Forms prepared for this study.

Assessment of Clinical Outcomes

Judgments about progression to severe or complicated malaria and the recurrence of uncomplicated malaria will be made by the Mali PI and a physician colleague (both blinded to the treatment the patient received) based on the CRFs and parasitologic data. As for the parasitologic data, those results will then be summarized by the subject's study numbers and returned to the study statistician who will place the data in groups by study arm (retaining blindedness by using Arm 1 and Arm 2 to identify the study arm rather than AQ-13 and Coartem) before the data are tested for differences and presented to the DSMB.

8 SAFETY ASSESSMENT AND REPORTING

8.1 Definition of an Adverse Event (AE)

An **adverse event** (AE) is any adverse change in health or side-effect that occurs in a person participating in a clinical trial while the patient is receiving the treatment (study medication) or within a pre-specified period of time after their treatment has been completed (in this case, within 6 weeks or 42 days).

8.2 Definition of a Serious Adverse Event (SAE)

An adverse event (AE) is serious and should be reported when the patient outcome is one or more of the following:

- Death,
- Life-threatening illness,
- Requires an inpatient hospitalization or the prolongation of an existing hospitalization,
- Results in persistent or permanent disability,
- Is associated with a congenital anomaly or birth defect,
- Requires intervention to prevent permanent impairment or damage. *Serious AEs do not include treatment failure with recurrent parasitemia and uncomplicated malaria (i.e., failure to clear asexual parasites from the bloodstream within 7 days or recurrence within 42 days).*

8.3 Definition of the Relatedness of AEs to DRUG TREATMENT

Definitions to be used in assessing the relationship of the investigational product to the AE/SAE are:

- **Unknown:**
Use this category only if the cause of the AE/SAE is not possible to determine.
- **Not Related:**
The subject did not receive the investigational product, the temporal sequence of the AE/SAE onset relative to administration of the investigational product is not reasonable, or there is another obvious cause of the AE/SAE.
- **Unlikely (to be Related):**
There is **no** evidence of exposure to the investigational product or there is another more likely cause of the AE/SAE.
- **Possibly Related:**
There is evidence of exposure to the investigational product, the temporal sequence of the AE/SAE onset relative to administration of the investigational product is reasonable, but the AE/SAE could have been due to another equally likely cause.
- **Probably Related:**
There is evidence of exposure to the investigational product, the temporal sequence of the AE/SAE onset relative to administration of the investigational product is reasonable, and the AE/SAE is more likely explained by the investigational product than by any other cause.
- **Definitely Related:**
There is evidence of exposure to the investigational product, the temporal sequence of the AE/SAE onset relative to administration of the investigational product is reasonable, the AE/SAE is more likely

explained by the investigational product than by any other cause, and the AE/SAE shows a pattern consistent with previous knowledge of the investigational product or investigational product class.

8.4 Assessment of Adverse Events

8.4.1 Detection of Adverse Events

Detection of adverse events (AEs) will be based on twice daily interviews during the inpatient stay and on interviews during each of the outpatient visits. At these times, the physician will ask about common symptoms such as headache, dizziness, nausea and any other symptoms or signs patients may have. Please note that patient diaries (which were used during the Phase 1 studies in New Orleans) are unlikely to be useful (although they will be offered) because we expect that > 90% of the study participants will be illiterate.

8.4.2 Assessment (Grading) of Adverse Events (AEs)

Based on the information in the patient's record and the Case Report Forms, the Mali PI and a physician colleague (blinded to the treatments that the patients have received) will grade the AEs observed and report those results by study number to the Study Statistician, who will provide those data to the DSMB grouped by study arm, but not identified in terms of which treatments the different study arms received.

8.5 Reporting Procedures

Researchers participating in clinical trials must report all adverse events to the Food and Drug Administration (FDA) or the relevant regulatory authority in the country where the drug is to be registered. Serious AEs must be reported immediately; minor AEs are 'bundled' by the sponsor and submitted later. Specific reporting procedures are summarized below for:

- Deaths – will be reported to the Medical Monitor, the Chair and other members of the DSMB, the Mali and Tulane IRBs and the FDA by phone within 24 hours of becoming aware of their occurrence and confirmed by E-Mail also within 24 hours of awareness of their occurrence.
- Non-fatal serious AEs (regardless of their relationship to the study protocol) - will be reported to the Medical Monitor and the Chair of the DSMB via E-Mail within 72 hours after becoming aware of their occurrence.
- Other Adverse Events (AEs) – AEs that do not result in death or life-threatening events, and are judged not to be serious will be accumulated (collated) as they occur and reported with annual and other regular reports to the Medical Monitor, Data Safety and Monitoring Board (DSMB), the Mali and Tulane IRBs and the FDA at regular intervals.

8.5.1 Serious Adverse Event Detection and Reporting

For events meeting the previously described definition of Serious Adverse Events, the completion of a Serious Adverse Event Form is required. Information on where to send this form is included in the Manual of Procedures for this study. All serious AEs will be followed through resolution by a study physician and reviewed by a Senior Investigator. Any AE considered serious by the PI or the Senior Investigator must be reported according to the guidelines on the Serious Adverse Event Form.

8.5.2 Reporting of Pregnancy

Please note that this section does not apply to this Proof of Concept Study for AQ-13 because enrollment in this study is restricted to males.

8.5.3 Procedures to be Followed in the Event of Abnormal Laboratory Test Values or Abnormal Clinical Findings

New abnormalities in chemistry or hematology test results during or after treatment with AQ-13 or Coartem will be graded based on the recent FDA Guidance for Healthy Adult and Adolescent Volunteers in Preventive Vaccine Trials [25]. Because a number of subjects will have abnormal chemistry and hematology laboratory values at admission because of malaria, the presence of abnormal laboratory values at the time of admission is not an exclusion from participation (unless those values require treatment), and the presence of abnormal laboratory values during treatment is an indication of an AE ONLY IF the initial laboratory values for that parameter were normal.

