8.6 Study Halting Rules

Because of the limited numbers of subjects in this study (**33** per study arm), halting rules based on statistical significance are likely to be of limited value. Therefore, the guidelines proposed below are based on the limited numbers of subjects likely to be evaluable and on the number, severity and relatedness of adverse events (AEs). If those guidelines are met for subjects in the arm receiving AQ-13, the enrollment of new subjects into the trial will be halted until the DSMB has had time to review the information available and thus to recommend whether the enrollment and treatment of adult Malian males who have uncomplicated malaria should continue with AQ-13 and Coartem in this study.

Table 4.

Temporary Halting Rules based on Adverse Events

Number	Severity of Adverse Event	Relatedness to Drug	Action(s) Taken
1 or more	Serious Adverse Event (SAE)	Probably or Definitely	Temporary Halt for DSMB Review
1 or more	Grade 4 Adverse Event	Probably or Definitely	Temporary Halt for DSMB Review
2 or more	Grade 3 Adverse Event	Probably or Definitely	Temporary Halt for DSMB Review

Table 5.

Temporary Halting Rules based on Efficacy (based on 15 subjects per study arm)

Control Coartem Result (number of failures)	AQ-13 Study Arm Result (number of failures)	Action(s) Taken
0 or 1 of 15	0 or 1 of 15	No action
0 or 1 of 15	2 or 3 of 15	No action
0 or 1 of 15	4 or 5 (or more) of 15	Temporary Halt for DSMB Review

In addition, summary data on efficacy (both blinded and separated by treatment group) will be presented to the DSMB at one pre-specified Interim Analysis for futility (after 15 patients have been enrolled in each treatment group/arm and have completed their follow-ups).

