14.1 Data Management Responsibilities

The responsibilities for data handling and record keeping as they relate to the sponsor, clinical site, laboratory and data coordinating center are outlined in Table 9, below. This information includes the roles of groups and individuals in data collection, review of data, study materials and reports and the retention of source documents, files and records. At the conclusion of the study, a copy of all data sets will be provided to DMID, FDA, the Mali Ministry of Health and other participating federal and international agencies. These data sets will be sent by the Information Technology director for this project, [name], at the Faculty of Science of the University of Bamako.

All source documents and laboratory reports will be reviewed by the clinical team and data entry staff in order to ensure they are accurate and complete. Adverse Events will be graded, assessed for severity and causality, and reviewed by the Principal Investigator and co-investigators (who will be blinded to the treatment arms to which the subjects were assigned).

Table 9.

Overview of Data Management Responsibilities

Data Management	Clinical Information	Clinical Lab Data	Holters	Molecular Results
Data Collection (Source Documents)	Screening, Enrollment CRFs and scans	Clin- Laboratory Data Printouts	Screen, Enroll, Holter reports	Initial & Follow-Up Lab reports
Data Review	as CRFs (StudyTRAX)	Printouts & CRFs	Holter reports	Lab rep's & CRFs
Data Entry, Cleaning	Bamako, StudyTRAX	Bamako, Tulane	Bamako	Bamako
Data Storage (source docs, electronic)	Bamako, Tulane	Bamako, Tulane	Bamako, Tulane	Bamako, Tulane
Initial Summary	Epidemiol, Mali PI	Epidemio, Mali PI	Cardiol Point G	Faculty of Science
Initial Data Review	Biostat, Clin Monitor	Clinical Monitor	Cardiol Mali	Mali PI
Additional Review	Tulane	Tulane	Cardiol Tulane	Sequence data
Evaluation, Grading of Adverse Events	PI, colleagues blind to treatment arm	PI, others blind to treatment arm	PI and Tulane Cardiology	Interpretation of recurrent infections
Reports	PI, Sponsor	PI, Sponsor	PI, Sponsor	PI, Sponsor
Long-term Storage	Hard copy, electronic	Mali and U.S.	Mali and U.S.	Mali and U.S.

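### Section 8.5.3 gives laboratory worsening from an abnormal admission value no route to being graded as an adverse event, which conflicts with Section 8.1

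*Combined protocol and SAP*

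**What the plan says.** Section 8.5.3 contains two rules. The first sets what is graded: "New abnormalities in chemistry or hematology test results during or after treatment with AQ-13 or Coartem will be graded", using a toxicity scale written for healthy vaccine-trial volunteers. The second sets what counts: the presence of "abnormal laboratory values during treatment is an indication of an AE ONLY IF the initial laboratory values for that parameter were normal". The stated reason is that "a number of subjects will have abnormal chemistry and hematology laboratory values at admission because of malaria". Such values do not bar enrolment unless they require treatment; exclusion criterion 3 in Section 5.2 gives Hb ≤ 7 gm/dL and K+ ≤ 3.5 mM as examples.

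Section 8.1 defines an AE as "any adverse change in health or side-effect that occurs in a person participating in a clinical trial", on treatment or within 42 days after it. It sets no condition on the subject's state at admission.

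Section 7.1.2 lists AEs first among the secondary outcomes. They are limited to events within 4 weeks that blinded physician reviewers judge possibly related to study drug. Section 10.3 compares AE frequency, the proportion of patients with AEs, and AE severity between the arms.

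**The concern.** The purpose of Section 8.5.3 is sound: an abnormality caused by malaria and present before dosing should not be charged to the drug. The wording goes further than that. It separates parameters by whether they were normal at admission, not by whether they got worse afterwards. A subject admitted with mild anemia whose hemoglobin then falls by several grades has suffered an adverse change, yet the value meets neither rule in Section 8.5.3.

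At stake is the completeness of the laboratory part of the AE endpoint in the first trial of AQ-13 in infected patients. Section 10.3 expects to conclude that the AEs of AQ-13 are similar to those of Coartem. Separating drug from disease is the task of the blinded relatedness review, and Section 8.5.3 removes these events before that review takes place.

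**Working it through.** The plan gives no figure on this point to reproduce. The check is a comparison of the two sections, followed by a small illustration.

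**Step 1. The possible courses of one laboratory parameter.**

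| Admission value | Post-dose value | Section 8.5.3 | Section 8.1 |
|---|---|---|---|
| Normal | Normal | Not an AE | Not an AE |
| Normal | Abnormal | Graded, counts | Can be an AE |
| Abnormal | Same or better | Not an AE | No adverse change |
| Abnormal | Worse, by any number of grades | Not graded, does not count | Can be an AE |

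The sections part only in the last row.

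**Step 2. Timing.** The only-if clause speaks of values during treatment. Drug is given on days 1 to 3, and the scheduled repeat panels are on day 4 (Section 6.5). Read literally, that clause may not reach the day 4 panel. The preceding sentence does reach it, because it covers values during or after treatment, but it is limited to new abnormalities. Neither sentence provides for worsening.

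**Step 3. Can the graders repair this?** Under Section 14.1, "All source documents and laboratory reports will be reviewed by the clinical team and data entry staff", and "Adverse Events will be graded, assessed for severity and causality, and reviewed by the Principal Investigator and co-investigators", blinded to arm. Section 8.4.2 likewise has blinded physicians grade from the patient record and the CRFs. So the values do reach the people who grade. The only criterion specific to laboratory values that the visible text gives them is Section 8.5.3. The CRFs, the Manual of Procedures and the part of the protocol between Section 8.6 and Section 9 were not available for this check.

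**Step 4. The route to the endpoint.** Section 8.3 rates an event as possibly related when another cause is equally likely, and as unlikely when another cause is more likely. Worsening for which malaria is the likelier cause would stay out of the endpoint under any recording rule. Worsening for which drug and malaria are equally likely would enter it if recorded. The loss to the endpoint is confined to the second kind and to anything rated higher.

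**Step 5. Illustration for one parameter.** The documents give no baseline shares or event rates, so both inputs are assumptions: p is the share of subjects abnormal at admission, and r is their risk of worsening relative to subjects normal at admission.

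- Subjects in an arm of 33 who cannot contribute a laboratory AE for that parameter: 33 × p.
- Share of that parameter's worsening that goes unrecorded: p × r / (p × r + 1 − p).

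| p | 33 × p | r = 0.5 | r = 1 | r = 2 |
|---|---|---|---|---|
| 0 | 0 | 0% | 0% | 0% |
| 0.3 | 9.9 | 0.15/0.85 = 18% | 0.30/1.00 = 30% | 0.60/1.30 = 46% |
| 0.5 | 16.5 | 0.25/0.75 = 33% | 0.50/1.00 = 50% | 1.00/1.50 = 67% |
| 0.7 | 23.1 | 0.35/0.65 = 54% | 0.70/1.00 = 70% | 1.40/1.70 = 82% |

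These shares illustrate the recording rule for a single parameter. They are not changes in the endpoint. The relatedness filter and the 4-week limit come afterwards, and a subject who has any other AE is already counted in the proportion of patients with AEs.

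**Step 6. Table 4.** The halting guidelines apply "If those guidelines are met for subjects in the arm receiving AQ-13" and need at least one SAE, at least one Grade 4 event or at least two Grade 3 events, in each case rated probably or definitely related. Removing events from a count can only make such a threshold harder to reach. If worsening from an abnormal admission value is never rated above possibly related, the rule removes nothing.

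**The case against.** The strongest reply is that Section 8.1 remains the definition of an AE, and that Section 8.5.3 speaks only of what indicates one. A blinded physician who sees a marked fall could still record an adverse change in health. This shows that the text can be read two ways, but it does not close the gap: a general definition does not displace an explicit rule written for laboratory values, and graders who follow the rule as written would not count the event.

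Other points stand and limit the matter:

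- The rule works parameter by parameter, so a subject's other parameters still count.
- Symptomatic or serious consequences are captured through the interviews in Section 8.4.1 and the definitions in Sections 8.1 and 8.2.
- Results that require treatment are excluded at entry, so for some parameters few or no subjects may be affected.
- Admission and follow-up values are collected and stored, so a shift table could be made at analysis and no data are lost.

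A reader might infer three stronger things, none of which the documents support:

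- **That the rule favors AQ-13.** It applies equally to both arms, allocation is random, and nothing in the documents shows that it acts unequally.
- **That the halting rules are materially weakened.** Only the direction is known. Any probability would rest wholly on invented event rates and relatedness shares.
- **That 18% to 82% of the AE endpoint is lost.** Those figures concern one parameter under assumed inputs.

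**Conclusion.** Section 8.5.3 is wrong as written, because it conflicts with Section 8.1 over worsening from an abnormal admission value. The consequence is possible under-counting, in both arms, of laboratory AEs that would otherwise go to relatedness review and, if judged at least possibly related within 4 weeks, enter the first-listed secondary endpoint. The size cannot be estimated from the documents. It is nil for a parameter that no subject has abnormal at admission, and it grows with the share who do. The effect on Table 4 is toward lower sensitivity, if there is any effect. Severity is modest: the primary endpoint is untouched, clinical consequences are still captured, and the raw values are kept. The conclusion assumes that the CRFs, the Manual of Procedures and the unavailable part of the safety section contain no rule for worsening.

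**What to change.** Reconcile Section 8.5.3 with Section 8.1:

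- Grade admission values on the scale already named for later values.
- Count a post-dose value, during or after treatment, as an AE if it is newly abnormal or at least one toxicity grade worse than at admission. If a different threshold is preferred, state it in advance.
- Say that abnormalities which persist or improve from admission do not count. This keeps the purpose of the present rule.
- Add a shift table of admission grade by worst post-dose grade, for each parameter and arm.
- Leave Table 4, including its counts and relatedness condition, as it is.

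The cost is a short wording change and one table. No new samples are needed: panels are planned at screening (Section 6.3), on day 4 (Section 6.5) and at recurrence (Section 6.7), and Flow Chart 4 appears to mark a further set in its 1/2-week column. Grading admission values is a new task. The drawback is somewhat more laboratory AEs to review, some of them due to malaria, on a scale meant for healthy volunteers; the relatedness review already exists to sort these.

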8.5.4 Type and Duration of the Follow-up of Subjects after Adverse Events

Mild AEs known to occur with both AQ-13 and malaria (e.g., headache, nausea, vomiting, myalgias, arthralgias) and other AEs will be followed daily until they have resolved and treated symptomatically as described in Table 2 on page 23 (acetaminophen for headache and for muscle and joint pains; antiemetics for nausea or vomiting).

8.6 Study Halting Rules

Because of the limited numbers of subjects in this study (**33** per study arm), halting rules based on statistical significance are likely to be of limited value. Therefore, the guidelines proposed below are based on the limited numbers of subjects likely to be evaluable and on the number, severity and relatedness of adverse events (AEs). If those guidelines are met for subjects in the arm receiving AQ-13, the enrollment of new subjects into the trial will be halted until the DSMB has had time to review the information available and thus to recommend whether the enrollment and treatment of adult Malian males who have uncomplicated malaria should continue with AQ-13 and Coartem in this study.

Table 4.

Temporary Halting Rules based on Adverse Events

Number	Severity of Adverse Event	Relatedness to Drug	Action(s) Taken
1 or more	Serious Adverse Event (SAE)	Probably or Definitely	Temporary Halt for DSMB Review
1 or more	Grade 4 Adverse Event	Probably or Definitely	Temporary Halt for DSMB Review
2 or more	Grade 3 Adverse Event	Probably or Definitely	Temporary Halt for DSMB Review

Table 5.

Temporary Halting Rules based on Efficacy (based on 15 subjects per study arm)

Control Coartem Result (number of failures)	AQ-13 Study Arm Result (number of failures)	Action(s) Taken
0 or 1 of 15	0 or 1 of 15	No action
0 or 1 of 15	2 or 3 of 15	No action
0 or 1 of 15	4 or 5 (or more) of 15	Temporary Halt for DSMB Review

In addition, summary data on efficacy (both blinded and separated by treatment group) will be presented to the DSMB at one pre-specified Interim Analysis for futility (after 15 patients have been enrolled in each treatment group/arm and have completed their follow-ups).

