QT	Interval from the beginning of ventricular depolarization (start of QRS) to the conclusion of repolarization (end of T wave)
QTc	QT interval adjusted (corrected) for heart rate
SAE	Serious Adverse Event
SOP	Standard Operating Procedure
t $\frac{1}{2}$	Half-Time (for concentration to decrease by 50%)
V_d	Volume of distribution (Liters)
WBC	White Blood Cell
WHO	World Health Organization
X	the percentage of the efficacy of the active control vs. placebo (C – P) that one desires to retain in the investigational drug (I) (see the Statistical Section on pages 37-40)

Title:	AQ-13 for Uncomplicated P. falciparum Malaria: Proof of Concept Study
Population:	Adult Malian males with uncomplicated Plasmodium falciparum Malaria This study will include adult Malian males ≥ 18 years of age in good general health (who have no known medical conditions other than malaria). Subjects who agree to participate and provide their informed consent will be randomized to one of two study arms (33 per arm \times 2 arms = 66 subjects) to receive either AQ-13 (1596 mg orally over 3 days) or Coartem (4 tabs twice daily \times 3 days).
Number of Sites:	There are several initial screening sites at: 1] the Missira/Sirakoroba Community Health Center in the Kolokani District and 2] referral outpatient clinics in and near Bamako. Although there is only one inpatient study site at the Clinical Research Center in Bamako, there will be two study follow-up sites for the 5 weeks of outpatient follow-up: the Community Health Center for Missira and Sirakoroba and the Clinical Research Center in Bamako.
Study Duration:	The duration of this study will be up to 15 months (including follow-up), beginning on June 15 th , 2013 and concluding on or before January 15, 2016.
Subject Duration:	The duration of each subject's participation will be 6 weeks, based on a 1 week inpatient stay for treatment/observation, plus 5 weeks of twice-weekly follow-up.

Primary Objective and Primary Endpoints:

1] The primary objective is to determine and compare the cure rates for AQ-13 and Coartem. Cure is a lack of recrudescence within 42 days (PCR-corrected) – no evidence of recrudescence with the same parasite genotype(s) after reduction of the asexual parasitemia to less than 25% of the admission value by day 3 and clearance of asexual parasites and fever by day 7. Failure is defined as lack of cure.

Secondary Objectives and associated Endpoints for comparisons of AQ-13 with Coartem:

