2.2 Rationale

Therefore, the next logical step in the evaluation of AQ-13 is to determine whether it is active against CQ-resistant *P. falciparum* infection in human subjects. The hypotheses underlying this protocol are that: 1] an AQ-13 dose of 1596 mg administered orally will be efficacious for the treatment of uncomplicated *P. falciparum* malaria in human subjects, and 2] the bioavailability, pharmacokinetics and adverse events (AEs) of AQ-13 in human subjects with uncomplicated malaria will be similar to those observed previously in healthy uninfected subjects during the Phase 1 studies [11].

The rationales for the selection of adult men for this Proof of Efficacy Study with AQ-13 are that: 1] the involvement of only males will obviate potential concerns about inadvertent pregnancies in female volunteers who have agreed to contraception and 2] that persons who have survived to adulthood in Mali are protected against life-threatening complications and death from malaria because they have acquired the semi-immune state [12]. Therefore, if for reasons we have not foreseen, AQ-13 does not work (if AQ-13 is not effective for treatment of uncomplicated malaria in human subjects), the risk of severe disease or death in these subjects will still be extremely low – because they are protected by their previous acquisition of the semi-immune state.

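### A death in the AQ-13 arm pauses enrolment automatically only if it is rated probably or definitely drug-related

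*Combined protocol and SAP*

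**What the plan says.** - **Section 8.2** defines seriousness by outcome ("An adverse event (AE) is serious and should be reported when the patient outcome is one or more of the following"), and death is first on the list. The exclusion at the end of that list covers treatment failure with recurrent parasitaemia and uncomplicated malaria, so it does not remove deaths.
- **Section 8.3** gives six relatedness ratings: unknown, not related, unlikely, possibly, probably and definitely. For a possibly related event, exposure and timing fit, "but the AE/SAE could have been due to another equally likely cause".
- **Section 8.5** deals with deaths separately and without regard to relatedness. They "will be reported to the Medical Monitor, the Chair and other members of the DSMB, the Mali and Tulane IRBs and the FDA by phone", and e-mail confirmation follows; both are due within 24 hours. No pause is mentioned.
- **Section 8.6** says that if its guidelines are met in the AQ-13 arm, "the enrollment of new subjects into the trial will be halted until the DSMB has had time to review the information available". Table 4 has three rows: one or more SAEs, one or more grade 4 events, and two or more grade 3 events. Each row requires the rating "Probably or Definitely". No row is specific to death.

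**The concern.** Every participant has acute malaria, so an alternative explanation for a death is always at hand. If a rater finds malaria and the drug equally likely, the correct rating under section 8.3 is possibly related, and Table 4 is silent. A death that AQ-13 caused can therefore fall below the trigger through correct use of the plan's own definitions.

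By the plan's account (section 2.2), earlier human experience with AQ-13 comes from healthy uninfected Phase 1 volunteers, and this study takes the drug into men with malaria. The same section says that, even if AQ-13 does not work, "the risk of severe disease or death in these subjects will still be extremely low". A death put down to malaria would contradict that safety premise, so it also deserves review before more men are dosed. Under the halting rule as written, enrolment could continue meanwhile.

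**Working it through.** **Tracing a death in the AQ-13 arm through the plan**

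| Rating (8.3) | Table 4 halt (8.6) | 24-hour report (8.5) | Pause attached to the report |
|---|---|---|---|
| Definitely | Yes | Yes | None |
| Probably | Yes | Yes | None |
| Possibly | No | Yes | None |
| Unlikely | No | Yes | None |
| Not related | No | Yes | None |
| Unknown | No | Yes | None |

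Two of six ratings halt enrolment and four do not. Two other rules might have closed the gap, but neither does:

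- Table 5 halts on efficacy. It needs at least 4 AQ-13 failures of 15, with 0 or 1 Coartem failures, so one death cannot trigger it.
- Section 6.8 stops an individual's treatment for an SAE possibly related to study drug. It does not pause enrolment. The threshold for stopping one man's dosing is thus lower than the threshold for pausing the trial after a death.

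The relatedness rating is also a weak gate. Section 10.3 has two physicians rate relatedness blinded to arm, yet a rating of probably requires evidence of exposure to the investigational product and a judgement that it is the likeliest cause. The sections available set no deadline for the rating.

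**How many men would start AQ-13 per week without a pause**

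The synopsis gives two durations in one sentence: "The duration of this study will be up to 15 months (including follow-up") and, after a start on June 15, 2013, "concluding on or before January 15, 2016". Each is used below. The last 42 days are taken off for follow-up, and 33 men go to AQ-13.

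- Calendar dates: 944 days; 944 − 42 = 902 days = 128.9 weeks; 33 / 128.9 = **0.26 per week**.
- Fifteen months: 15 × 30.44 − 42 = 415 days = 59.2 weeks; 33 / 59.2 = **0.56 per week**.
- Ceiling from bed capacity (8–10 beds in section 5.1, 5–7 day stay in section 6.6): admissions per week = beds × 7 / stay, from 8 × 7 / 7 = 8 to 10 × 7 / 5 = 14. Half go to AQ-13, so 4 to 7 per week. At that pace all 66 men would be enrolled in 66 / 14 = 4.7 to 66 / 8 = 8.3 weeks, so this is an upper bound only.

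**What an any-death row would cost**

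The chance of at least one background death among 33 men is 1 − (1 − b)^33. The documents give no background death rate b, so it is assumed:

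| Assumed b | Chance of a pause for a background death |
|---|---|
| 0.05% | 1.6% |
| 0.1% | 3.2% |
| 0.2% | 6.4% |

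The benefit cannot be computed. The documents do not say how often a drug-caused death would be rated below probably.

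**The case against.** There are four substantial counter-arguments.

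1. **The deciding section may be one not seen here.** Section 4 points to section 8.7 for the DSMB, which is a natural place for a rule on deaths. This stands as a limit on the finding. It does not alter Table 4, which sets an explicit threshold and does not refer to a separate rule for deaths.
2. **Deaths already get special handling.** They go by phone within 24 hours to the Medical Monitor, the whole DSMB, both IRBs and the FDA. Non-fatal SAEs go by e-mail within 72 hours to the Medical Monitor and DSMB Chair. Nothing seen bars the DSMB from recommending a pause. This stands, and it reduces the gap to automatic versus prompted. On the average pace, the 24-hour reporting window covers only about 0.04 to 0.08 AQ-13 men (0.26 / 7 to 0.56 / 7), or 0.6 to 1 at the bed ceiling. But the window covers reporting only, and the text seen sets no time for the review that follows.
3. **The causal argument cuts both ways.** If death from malaria is so unlikely in these men, raters should lean towards the drug, and Holter recordings on days 1–4 would help to identify a cardiac death during dosing. This has some force. It still relies on a blinded judgement in a single case, and a death rated as malaria would itself be unexpected on the plan's own premise.
4. **Conditioning on relatedness is deliberate.** Section 8.6 says its guidelines rest on the number, severity and relatedness of events, and stopping one man's treatment is a different decision from pausing a trial. This is fair for SAEs in general. It is less persuasive for death, where the halt is temporary and cheap and the alternative is dosing more men.

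**Conclusion.** The concern holds. In the sections available, an AQ-13-arm death pauses enrolment automatically under only two of the six relatedness ratings, and the 24-hour death report carries no pause. The death would be known to the DSMB; what is missing is the automatic halt.

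The average exposure is small, about 0.26 to 0.56 men newly given AQ-13 for each week that review lasts. These averages assume even recruitment. Section 5.1 places the heavy Bamako clinic attendance in August to November, so the pace in season could be higher, up to the bed ceiling of 4 to 7 per week. The benefit is not quantified. The change is worth making because the outcome is the gravest one and the fix is cheap. Confidence is medium, mainly because section 8.7 could not be read.

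**What to change.** Add one row to Table 4:

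| Number | Severity | Relatedness | Action |
|---|---|---|---|
| 1 or more | Death in the AQ-13 arm | Any, including unknown | Temporary halt pending DSMB review |

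If section 8.7 already provides this, cross-refer to it from Table 4 instead.

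The row uses the existing DSMB, 24-hour death report and temporary halt. It changes no sample size, alpha or endpoint, and it can act on the death report without waiting for a relatedness rating. The one downside is a temporary pause for a death that the DSMB then judges unrelated, at the 1.6% to 6.4% chance shown above for the assumed background rates.
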